##### ECOGs

Performance status is assessed according to ECOG criteria at timepoints throughout the study. The ECOG criteria is summarised in section 8.2.2. of the CSP.

##### 4.2.1.8.2 Presentations

###### Maximum Tolerated Dose Evaluation (applicable to Substudy 1 Part A only)

The MTD evaluation is based on the DLT evaluable population. The number and percentage of participants with DLT during dose escalation are presented by dose level.

##### ECOGs

The number and percentage of each participant in each ECOG category will be displayed by each timepoint.

## 4.2.2 Secondary Endpoint: Objective Response Rate

A secondary efficacy endpoint is objective response rate (ORR).

### 4.2.2.1 Definition

The ORR is programmatically derived based on the site investigator RECIST v1.1 data, and using all scans regardless of whether they were scheduled or not.

Objective Response (OR) is defined as a programmatically derived, confirmed best overall response of Complete Response (CR) or Partial Response (PR) that occurs prior to the initiation of subsequent anticancer treatment and prior to progression. ORR is defined as the percentage of participants with OR.

A confirmed response of CR/PR means that a response of CR/PR is recorded at 1 visit and confirmed by repeat imaging not less than 4 weeks after the visit when the response was first observed with no evidence of progression between the initial and CR/PR confirmation visit. Data obtained up until progression, or last evaluable assessment in the absence of progression, are included in the assessment of ORR. Also, only data obtained before the start of subsequent anticancer treatment (excluding radiotherapy) are included. Therefore, both visits contributing to a confirmed response must be prior to progression and prior to subsequent anticancer treatment.

In the case where a participant has two non-consecutive visit responses of PR, then, if the time between the 2 visits of PR is greater than 4 weeks and there is no progressive disease between the PR visits, then a best response of PR is assigned. Similarly, if a participant has visit responses of CR, Not Evaluable (NE), CR, then, as long as the time between the 2 visits of CR is greater than 4 weeks, then a best response of CR is assigned.

In cases where CRC subjects may undergo potentially curative surgery at some point following treatment, an additional summary of responses will be provided to distinguish between surgically and drug-only induced responses as follow:

- ORR where only responses prior to curative surgery are included in the numerator (secondary endpoint described in previous section).
- ORR where subjects who have surgery that results in the absence of any tumour after surgery are treated as a CR and are included in the numerator.

Subjects receiving surgery should continue to be followed up for objective disease progression as defined by RECIST v1.1.

Overall visit response post curative surgical intervention derivation is described in section [7 Appendices](#).

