Any concurrent chemotherapy, radiotherapy, immunotherapy, or biologic or hormonal therapy for cancer treatment other than those under investigation in this study	Should not be given concomitantly while the participants are on study intervention, unless specified in a Substudy. (Concurrent use of hormones for non-cancer-related conditions [eg, insulin for diabetes and hormone replacement therapy] is acceptable. Local treatment of isolated lesions for palliative intent may be acceptable [eg, by local surgery or radiotherapy]) upon consultation with study physician.	
Live attenuated vaccines	Should not be given through 30 days after the last dose of study intervention	
Immunosuppressive medications including, but not limited to, systemic corticosteroids at doses exceeding 10 mg/day of prednisone or equivalent, methotrexate, azathioprine, and tumour necrosis factor-α blockers	Should not be given concomitantly or used for premedication prior to the immunotherapy infusions. The following are allowed exceptions: Use of immunosuppressive medications for the management of study intervention-related AEs Short-term premedication for participants receiving combination agent where the prescribing information for the agent requires the use of steroids for documented hypersensitivity reactions Use in participants with contrast allergies In addition, use of inhaled, topical, and intranasal corticosteroids is permitted A temporary period of steroids will be allowed if clinically indicated and considered to be essential for the management of non-immunotherapy related events experienced by the participant (eg, chronic obstructive pulmonary disease, radiation, nausea, etc)	
Metformin	Metformin has been shown to induce GDF15 gene expression, thereby elevating circulating GDF15 levels significantly. One study showed that a one-time dose of metformin increased mean circulating GDF15 levels about 2.5-fold (Coll et al, 2020). To prevent falsely high GDF15 level results, participants must not take metformin for at least 72 hours prior to the screening GDF15 blood sample and should be switched to an acceptable alternative; the participant must demonstrate controlled diabetes mellitus on this	

Table 8 Prohibited Concomitant Medications

Prohibited Medication/Class of Drug	Usage	
	alternative at least 7 days prior to starting the study intervention on Cycle 1 Day 1.	
Herbal and natural remedies	Should not be given concomitantly unless agreed by the Sponsor	

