Abbreviations: AE = adverse event; CTLA-4 = cytotoxic T-lymphocyte associated antigen; PD-1 = programmed cell death-1; PD-L1 = programmed cell death ligand-1.

Table 9 Permitted Concomitant Medications

Supportive Medication/Class of Drug	Usage	
Premedication for management of diarrhoea, nausea, and vomiting	Permitted after but not before the first dose of study intervention	
Blood transfusions	Permitted at any time during the study	
Erythropoietin	Prophylactic erythropoietin should not be started during Cycle 1 of the study but may be started during Cycle 2 and after. Participants already receiving erythropoietin at the time of screening may continue it provided they have been receiving it for more than one month at the time study treatment has started.	
G-CSF	G-CSF should not be used prophylactically during Cycle 1, but may be considered after Cycle 1	
Megestrol acetate	Permitted for appetite stimulation	
Bisphosphonates, and denosumab	Permitted for treatment of bone metastases	
Concomitant medications or treatments (eg, acetaminophen or diphenhydramine) deemed necessary to provide adequate prophylactic or supportive care, except for those medications identified as "prohibited," as listed in Table 8	To be administered as prescribed by the Investigator	
Best supportive care (including antibiotics, nutritional support, correction of metabolic disorders, optimal symptom control, and pain management [including palliative radiotherapy to non-target lesions, etc])	Should be used, when necessary, for all participants	
Inactivated viruses, such as those in the influenza vaccine, and COVID-19 vaccine	Permitted. COVID-19 vaccination should not be given for 72 hours prior to administration of the first dose of AZD8853 or during the DLT period.	

Abbreviations: DLT = dose limiting toxicity; G-CSF = granulocyte colony stimulating factor, COVID-19 = coronavirus disease 2019.

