9.4.3 Efficacy Analyses

The efficacy endpoints for tumour response (ORR, DCR at 15 weeks, DoR, and percentage change in tumour size) will be summarised for the Response Evaluable Population using RECIST v1.1 by Investigator assessment. The efficacy endpoints of PFS and OS will be summarised on the Safety Population.

Additional subgroup analysis of efficacy may be performed as specified in the SAP.

The RECIST tumour response data will be used to programmatically determine each participant's visit response and derive the endpoints ORR, DoR, DCR at 15 weeks, percentage change in tumour size, and PFS.

Best Overall Response

The BoR is calculated based on the overall visit responses from each RECIST assessment. It is the best response a participant has following start of treatment but prior to starting any subsequent cancer therapy and up to and including RECIST progression or the last evaluable assessment in the absence of RECIST progression. Categorisation of BoR will be based on RECIST using the following response categories: CR, PR, SD, progressive disease, and NE.

Objective Response Rate

The ORR is defined as the percentage of participants with a confirmed CR or PR, with the denominator defined as the number of participants in the Response Evaluable Population. Objective response rate and its 90% CIs (Clopper Pearson method; Clopper et al, 1934) will be summarised.

Duration of Response

The DoR is defined as the time from the date of first documented response (which is subsequently confirmed) until the date of documented progression or death in the absence of disease progression. The time of the initial response will be defined as the latest of the dates contributing towards the first visit that was CR or PR that was subsequently confirmed. Participants who have not progressed or died at the time of analysis will be censored at the time of the latest date of assessment from their last evaluable RECIST assessment.

It will be summarised using descriptive statistics and Kaplan-Meier plots, where there are sufficient numbers of responders.

Disease Control Rate at 15 Weeks

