### **4.2.3 Best Overall response**

#### **4.2.3.1 Definition**

BOR is calculated based on the overall visit responses from each RECIST v1.1 assessment, described in Appendix A (Section [7.1](#)). It is the best response a participant has had following start of IP, but prior to starting any subsequent cancer therapy and up to and including RECIST v1.1 progression or the last evaluable assessment in the absence of RECIST v1.1 progression. Categorization of BOR is based on RECIST v1.1 using the following response categories: CR, PR, Stable Disease (SD); progressive disease; and NE.

BOR is determined programmatically based on RECIST v1.1. using all site investigator data up until the first progression event (i.e., progression or death). For participants whose progression event is death, BOR is calculated based upon all evaluable RECIST v1.1 assessments prior to death.

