#### **4.2.3.2 Derivations**

For participants who die with no evaluable RECIST v1.1 assessments, if the death occurs  $\leq$  15 weeks (i.e. 14 weeks [5 weeks + 9 weeks] + 1 week to allow for a late assessment within the assessment window) after first dose of IP, then BOR is assigned to the progressive disease

category. For participants who die with no evaluable RECIST v1.1 assessments, if the death occurs > 15 weeks after first dose then BOR is assigned to the NE category.

For CR/PR, the initial overall visit assessment that showed a response uses the latest of the dates contributing towards a particular overall visit assessment. A participant is classified as a responder if the RECIST v1.1 criteria for a CR or PR are satisfied at any time following first IP dose, prior to RECIST v1.1 progression and prior to starting any subsequent cancer therapy. CR or PR must be confirmed (see detail in Objective Response Section [4.2.2.1](#)).

For determination of a best response of SD, the earliest of the dates contributing towards a particular overall visit assessment is used. SD should be recorded at least 5 weeks (5 x 7 = 35 days) from first dose.

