##### **4.2.7.1 Definition**

This is based on RECIST v1.1 TL measurements taken at baseline and each post-baseline assessment. Tumour size is the sum of the longest diameters (or short axis measurements for

lymph nodes) of the TLs. Baseline for RECIST v1.1 is defined to be the last evaluable assessment prior to first IP dose.

An outcome endpoint for this study is percentage change from baseline in TL tumour size at each post-baseline assessment e.g., at Study week 15.

The tumour size and percentage change from baseline in the sum of tumour size at each assessment are calculated. The best change in tumour size from baseline (i.e., depth of response) is the largest decrease from baseline or the smallest increase from baseline in the absence of a reduction and includes all assessments:

- up to and including the first visit at which the overall visit response is progressive disease,
- prior to death in the absence of progression,
- prior to the start of subsequent anti-cancer therapy (including radiotherapy)
- or up to and including the last evaluable RECIST v1.1 assessment if the participant has not died, progressed, or started subsequent anti-cancer therapy.

Each post-baseline disease assessment for a participant that meets the following conditions are included: all TLs identified at baseline have measurements recorded at the current visit (i.e., they cannot be not done or not evaluable). If a lesion is recorded as  $\leq 5$ mm then this is used in the calculations.

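### ORR, BOR and best tumour-size change use different radiotherapy cut-offs in the SAP, so a response after radiotherapy to a non-target lesion can count in one output and not in another

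*SAP*

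**What the plan says.** SAP 4.2.2.1 gives this definition of objective response: "programmatically derived, confirmed best overall response of Complete Response (CR) or Partial Response (PR) that occurs prior to the initiation of subsequent anticancer treatment". That sentence does not mention radiotherapy. The next paragraph then says which data count: "only data obtained before the start of subsequent anticancer treatment (excluding radiotherapy) are included".

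BOR, on which objective response rests, has no such carve-out. SAP 4.2.3.1 takes the best response after the start of treatment "but prior to starting any subsequent cancer therapy and up to and including RECIST v1.1 progression". SAP 4.2.3.2 repeats the limit ("prior to RECIST v1.1 progression and prior to starting any subsequent cancer therapy") and refers to 4.2.2.1 for the confirmation rule. Protocol 9.4.3 also ends BOR at data "prior to starting any subsequent cancer therapy". None of these places says whether radiotherapy is a subsequent cancer therapy.

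SAP 4.2.7.1 takes the opposite line to the ORR text for best change in tumour size: only assessments "prior to the start of subsequent anti-cancer therapy (including radiotherapy" are used.

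Some radiotherapy during study treatment is foreseen. In protocol 6.5, Table 8 says "Local treatment of isolated lesions for palliative intent may be acceptable" after consultation with the study physician, and Table 9 lists "palliative radiotherapy to non-target lesions" among supportive measures.

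**The concern.** These endpoints are read from the same scans of the same participants, so they should stop at the same point. As written, one participant can be a confirmed PR in the ORR table and still have a waterfall bar that never reaches the −30% reference line, which SAP 4.2.7.3 ties to partial response. The BOR table could side with either.

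ORR is the quantity whose precision sets the Part C sample size (SAP 3.3.7.2), and it is read at the interim look for lack of efficacy. Responders also feed duration of response (SAP 4.2.5). With no randomised comparator, there is nothing against which to judge a response first seen after radiotherapy. For colorectal participants, SAP 4.2.2.1 already separates surgical from drug-only responses. It has nothing equivalent for radiotherapy.

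**Working it through.** The plan's own ORR precision example in SAP 3.3.7.2 is redacted, so there is no stated figure to reproduce.

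**Step 1: the cut-offs side by side**

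| Endpoint | Place | Does radiotherapy close the window? |
|---|---|---|
| ORR, data included | SAP 4.2.2.1 | No |
| Objective response, definition | SAP 4.2.2.1 | Not stated |
| BOR | SAP 4.2.3.1, 4.2.3.2; protocol 9.4.3 | Not stated |
| DCR at study week 15 | SAP 4.2.4.1, 4.2.4.2 | Not stated |
| Best tumour-size change | SAP 4.2.7.1 | Yes |

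**Step 2: where the difference can matter**

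- *Target lesion irradiated.* SAP 7.1 treats the lesion as intervened for the rest of the study. Each later visit is progressive disease or NE, so no later CR or PR can be counted, whatever 4.2.2.1 says.
- *Non-target lesion or another site irradiated.* The intervention rule in SAP 7.1 covers target lesions only, and SAP Table 11 has no counterpart for non-target lesions. Under SAP Table 12, a target-lesion PR with a non-progressing non-target status and no new lesion is an overall PR. The visit stays countable for ORR. Radiotherapy could also hold back a non-target progression that would otherwise have made the visit progressive.

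Only the second case is open.

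**Step 3: an invented participant in the open case**

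Target-lesion sums are 100 at baseline, 85 at study week 6, 68 at week 15 and 65 at week 24. A non-target lesion is irradiated on Day 60. There is no progression or new lesion.

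- Changes from baseline: (85 − 100)/100 = −15%; (68 − 100)/100 = −32%; (65 − 100)/100 = −35%.
- ORR under the carve-out: PR at week 15, confirmed 9 weeks later (at least 4 are needed). Responder.
- Best tumour-size change, radiotherapy closing the window: −15%.
- BOR, if radiotherapy is a subsequent cancer therapy: SD. If it is not: PR.
- DCR, if radiotherapy is a subsequent cancer therapy: SD is credited for at most 60 days, short of 14 × 7 = 98. No disease control. If it is not, the confirmed PR gives disease control.

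**Step 4: scale**

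The exact two-sided 90% Clopper-Pearson interval (SAP 4.2.2.4) has lower limit Beta(0.05; x, n − x + 1) and upper limit Beta(0.95; x + 1, n − x). Responder counts are assumed.

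- n = 40, one participant = 1/40 = 2.5 points: 3/40 = 7.5% (2.1–18.3) versus 4/40 = 10.0% (3.5–21.4).
- n = 20 (interim), one participant = 1/20 = 5 points: 1/20 = 5.0% (0.3–21.6) versus 2/20 = 10.0% (1.8–28.3).

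**The case against.** Much of the case for leaving the text alone is sound.

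- *Irradiated measured lesions are already handled.* A reader might infer that shrinkage of an irradiated target lesion is credited to AZD8853. SAP 7.1 prevents this. A counted response still needs at least 30% shrinkage in target lesions that were not irradiated, so it would also be too strong to say such a response cannot be due to the drug.
- *Objective response is BOR by definition.* A reader might infer that ORR will exceed the CR plus PR count. That happens only if the two are programmed separately and BOR is taken to stop at radiotherapy. If ORR is read off BOR, the counts agree. But the carve-out then has no effect of its own unless BOR is given the same rule, which it is not. Two programmers could each follow the text and differ.
- *The carve-out can be defended.* Permitted palliative radiotherapy during treatment need not be a subsequent anticancer treatment, and stopping at it could discard real responses in participants still on AZD8853. This stands as a reason not simply to swap the word excluding for including. The SAP does not state this reasoning, and it does not explain why tumour size follows the opposite rule.
- *Protocol departure.* A reader might infer that the SAP departs from the protocol without declaring it. The protocol's cut-off sits in its BOR definition, and its ORR definition states none, so this is not established.
- *Tables 8 and 9.* A reader might infer that they conflict over treating target lesions. Table 9's wording is illustrative rather than restrictive, so a conflict is not shown.

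ORR is also a secondary endpoint with no hypothesis test. That limits the harm to estimation and to decisions based on the estimate.

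**Conclusion.** The inconsistency is real and narrow. The ORR and tumour-size rules treat radiotherapy in opposite ways, and the BOR and DCR rules do not say. The effect is confined to participants who have radiotherapy to a non-target lesion or another site and then respond in unirradiated target lesions, or whose non-target progression is masked. Each is worth 2.5 points of ORR at n=40 and 5 points at the n=20 interim.

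This assumes that such radiotherapy is treated as falling within subsequent therapy, as the parentheses in 4.2.2.1 and 4.2.7.1 both imply. If it never does, the two rules do not clash in practice, but the SAP does not say so. How many participants would be affected cannot be estimated from the documents. The point merits correction before the analysis; it does not show that the ORR will be materially wrong.

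**What to change.** 1. Derive one start-of-subsequent-anticancer-therapy date per participant. State once whether palliative radiotherapy to a non-target lesion sets it, and use that date for ORR, BOR, DCR at study week 15 and best tumour-size change.
2. Take ORR directly from BOR, and cross-refer to SAP 7.1 for irradiated target lesions.
3. If the radiotherapy carve-out is kept, apply it to all four endpoints, list every response first seen after radiotherapy, and add a sensitivity ORR that stops at any radiotherapy.

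The cost is SAP wording, one shared derived date and, if the carve-out stays, one listing and one extra ORR summary. The data are already collected. The ORR that stops at any radiotherapy may be slightly lower.

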8.1 Efficacy Assessments

RECIST v1.1 guidelines for measurable, non-measurable, TLs and NTLs, and the objective tumour response criteria are presented in Appendix F of this CSP. Tumour assessments will be based on RECIST v1.1 (Eisenhauer et al, 2009) and will be performed according to the schedule presented in each Substudy.

Standard radiographic imaging using RECIST is used to assess both response (in participants with measurable disease) and progression. An ORR as per RECIST v1.1 criteria requires confirmation of PR and CR and must occur no fewer than 4 weeks after initial documentation of PR or CR. Disease progression will be defined as per RECIST v1.1; however, if the participant is clinically stable, a confirmatory scan for progression is left up to the discretion of the Investigator.

Tumour assessments use images from CT (preferred) or MRI, with i.v. contrast, of the chest, abdomen, and pelvis, and should additionally investigate areas that may be involved based on signs and symptoms of individual participants, collected during screening/baseline and at regular (follow-up) intervals during study intervention. Brain scans (MRI preferred) are mandatory at screening/baseline for all NSCLC participants in this study, participants with known brain metastasis, and as clinically indicated for other participants. Post-baseline MRI of the brain will only have to be performed in participants with brain metastases at baseline, while participants without brain metastases do not need additional brain scans for subsequent tumour assessments unless clinically indicated. The imaging modality used for baseline

tumour assessment should be kept the same consistently at each subsequent follow-up assessment throughout the study if possible. It is important to follow the tumour assessment schedule as closely as possible (refer to the SoA in the respective Substudy) relative to dose of study intervention.

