Screening/baseline imaging should be performed no more than 28 days before start of study intervention and ideally should be performed as close as possible to and prior to the start of study intervention. Scans obtained as part of standard clinical practice, prior to informed consent, but within the 28-day period are acceptable. Tumour assessments should be performed per the SoA in the respective Substudy until objective disease progression as defined by RECIST v1.1 (refer to Appendix F) and assessed by the Investigator, or withdrawal of consent. Response (CR or PR) should be confirmed by a repeat, consecutive scan at least 4 weeks after the first documentation of response.

If the Investigator is in doubt as to whether progression has occurred, particularly with response to NTLs or the appearance of a new lesion, it is advisable to continue treatment until the Investigator reassesses the participant's status at the next scheduled assessment (confirmation), or sooner if clinically indicated. Scans confirming progression should not be conducted within 1 week after a progression biopsy to allow for reduction in inflammation.

If scans are performed outside of scheduled visit window and the participant has not progressed, every attempt should be made to perform the subsequent scans at their scheduled visits whilst the participant remains on study treatment. If the participant interrupts treatment or incurs a treatment delay, scans should continue to occur at the protocol-defined frequency. It is important to follow the SoA as closely as possible.

Tumour markers will not be used for tumour response assessments as per RECIST v1.1. Tumour markers should be obtained as per standard-of-care.

Storage of Scans

Sites will be required to store electronic copies of all scans (CT, or other scans for efficacy, and PET scans), and the Sponsor will arrange for centralized storage of all imaging data. All imaging assessments, including unscheduled visit scans, will be collected on an ongoing basis, and sent to the Sponsor or designee for storage. The centralized storage of imaging data would allow independent centralized third party blinded review of disease assessments. In this regard, and at the discretion of the Sponsor, an independent central review of all scans used in the assessment of tumours by RECIST v1.1 may be conducted. Guidelines for imaging collection and storage will be provided in a separate document.

Skeletal Muscle Index

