##### 4.2.5.2 Derivations

$$\text{DoR (Months)} = \frac{(\text{Date of PFS event or censoring-date of first OR that is subsequently confirmed}) + 1}{(\frac{365.25}{12})}$$

where PFS event is progression or death.

The end of response should coincide with the date of progression or death from any cause used for the PFS endpoint. The time of the initial response is defined as the latest of the dates contributing towards the first visit response of CR or PR (which was subsequently confirmed). If a participant does not progress following a response, then their DoR is censored on the PFS censoring date. Only participants who have achieved OR (confirmed CR or confirmed PR) are evaluated and summarised for DoR.

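### The SAP confirms a partial response on two non-consecutive scans, while the protocol says the confirming scan should be consecutive; the difference is undeclared and can only raise ORR

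*SAP*

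**What the plan says.** Protocol 8.1 makes confirmation a condition of objective response: "An ORR as per RECIST v1.1 criteria requires confirmation of PR and CR and must occur no fewer than 4 weeks after initial documentation". Later in the same section it says how the scans should follow one another: "Response (CR or PR) should be confirmed by a repeat, consecutive scan at least 4 weeks after the first documentation of response". The statistical definition in protocol 9.4.3 adds no rule of its own: "The ORR is defined as the percentage of participants with a confirmed CR or PR, with the denominator defined as the number of participants".

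SAP 4.2.2.1 opens with a general rule under which a response is "confirmed by repeat imaging not less than 4 weeks after the visit when the response was first observed with no evidence of progression between" the two visits. It does not ask that the scans be consecutive. It then covers the non-consecutive case directly, in a sentence that begins "In the case where a participant has two non-consecutive visit responses of PR, then, if the time between the 2 visits of PR is". The rest of that sentence sets the condition and the result: "greater than 4 weeks and there is no progressive disease between the PR visits, then a best response of PR is assigned". A parallel sentence accepts CR-NE-CR.

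Two other endpoints take up this rule. For best overall response (BOR), SAP 4.2.3.2 says "CR or PR must be confirmed (see detail in Objective Response Section" 4.2.2.1). For DoR, SAP 4.2.5.2 says "The time of the initial response is defined as the latest of the dates contributing towards the first visit response of CR or PR", provided that visit was later confirmed, and limits DoR to confirmed responders.

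SAP Section 2 lists three changes from the protocol: the end-of-study definition, the screen-failure definition, and the data shown at the end of Part A. The confirmation rule is not among them. SAP 4.2.2.5 plans no sensitivity analysis of ORR.

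**The concern.** The two documents give different rules for what makes a PR confirmed. Under the SAP only progression between two PRs breaks confirmation. An evaluable scan that shows SD, and so fails to confirm the response, is passed over if a later scan shows PR again. A lesion sum that moves back and forth across the 30% shrinkage threshold can then become an objective response.

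SAP 3.3.7.2 sizes each Part C expansion for precision in estimating ORR and intends its confidence intervals to inform decisions on future studies. A rule that adds responders, is not declared, and has no planned comparison with the protocol rule affects that estimate. Visit responses are listed, but a reader who wanted ORR under the protocol rule would have to recount by hand.

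**Working it through.** **No plan figure to reproduce.** The ORR precision examples in SAP 3.3.7.2 are redacted, and no power or error rate depends on this rule. The check is a comparison of the two rules, followed by the effect of one participant on ORR.

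**Step 1. Scan days.** With Cycle 1 Day 1 as study day 1, study weeks 6, 15 and 24 begin on days 5×7+1 = 36, 14×7+1 = 99 and 23×7+1 = 162. The first and third scans are 162 − 36 = 126 days apart, or 18 weeks, which exceeds the SAP's 4 weeks.

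**Step 2. Apply both rules.** With PR, SD or NE possible at each of three scheduled scans there are 3³ = 27 sequences.

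- SAP rule (any two PRs more than 4 weeks apart, no progression between): every sequence with at least two PRs, 3×2 + 1 = 7.
- Protocol 8.1 wording (two adjacent PRs at least 4 weeks apart): 3 + 3 − 1 = 5.
- Difference: 7 − 5 = 2 sequences.

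| Sequence | SAP 4.2.2.1 | Protocol 8.1 wording |
|---|---|---|
| PR-SD-PR | confirmed | not confirmed |
| PR-NE-PR | confirmed | not confirmed |

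No sequence is confirmed under the protocol wording but not under the SAP, so the departure can only raise ORR.

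**Step 3. Effect on ORR.** Inputs: n = 40 per expansion (protocol 10.9.2 and SAP 3.3.7.2), all taken as response evaluable, and the two-sided 90% Clopper-Pearson interval of SAP 4.2.2.4. The lower limit is the 5th percentile of Beta(x, n−x+1); the upper is the 95th percentile of Beta(x+1, n−x). One participant is worth 1/40 = 2.5 points. The responder counts are assumed.

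| Responders | ORR | 90% CI |
|---|---|---|
| 3/40 | 7.5% | 2.1 to 18.3% |
| 4/40 | 10.0% | 3.5 to 21.4% |
| 5/40 | 12.5% | 5.1 to 24.5% |

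If the SAP rule gives 4 responders and one is PR-SD-PR, the consecutive rule gives 3. If it gives 5 and two are of that kind, the consecutive rule again gives 3.

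**Step 4. Other endpoints.** BOR changes from PR to SD for a three-scan PR-SD-PR. DoR gains a participant whose start date is the first PR. Disease control is unaffected in the three-scan example: SAP 4.2.4.2 counts unconfirmed responders through duration of SD, and a participant progression-free at day 162 is past 14 weeks (98 days).

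**The case against.** The best defence is that the protocol is softer than the conflict suggests. The word *consecutive* appears once, in the imaging section, governed by *should*. The sentence that makes confirmation mandatory asks only for the 4-week interval, the statistical definition asks only for confirmation, and protocol 9.4 leaves technical detail to the SAP. This stands to the extent that it would be too strong to say the protocol mandates consecutive scans. But that sentence is the protocol's only statement on how the scans should follow one another, and the SAP contradicts it rather than adding detail.

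The effect is also limited. ORR is secondary and descriptive, with no hypothesis test and no comparison between cohorts. The intervening SD must fall short of progression from nadir (at least 20% and 5 mm). Some non-consecutive pairs are harmless, for example when an unscheduled PR scan less than 4 weeks after the first falls between two PRs. All of this stands.

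Three stronger readings are tempting but not supported:

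- *The SAP is laxer for PR than for CR because its CR example allows only NE between.* SAP Appendix A says only CR, progressive disease or NE can follow a target-lesion CR, so naming NE there follows from the algorithm.
- *DoR is inflated by 18 weeks.* Both documents run DoR to progression or death, so time spent in SD belongs to it by definition. Without later confirmation, a PR-SD-PR participant has no DoR under the consecutive rule, so there is nothing to measure a gain against. Because unscheduled scans count, 18 weeks is not a minimum gap either. Adding such a participant could move the median DoR in either direction.
- *The interim ORR moves by 5 points (1/20 to 2/20).* That is the value of one participant, but PR-SD-PR needs three scans and the interim is triggered by the opportunity for two. Only earlier enrolees with a third scan, or participants with unscheduled scans, could contribute.

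**Conclusion.** The point holds as an undeclared conflict between SAP 4.2.2.1 and protocol 8.1. The SAP accepts PR-SD-PR and PR-NE-PR as confirmed; the protocol's wording does not. Relative to the consecutive rule the SAP can only raise ORR, by 2.5 points per affected participant at n = 40, and it admits those participants to the DoR set from their first PR. The main concern is the intervening evaluable SD. The literal wording also excludes an intervening NE, for CR as well as PR.

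The size rests on assumed responder counts and on 40 response-evaluable participants per expansion. The documents give no basis for estimating how many participants would show these patterns. No conclusion is drawn on the direction of any DoR effect or on the size of an effect at the interim.

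**What to change.** **Preferred.** For the main ORR, BOR and DoR, rewrite the paragraph in SAP 4.2.2.1 to follow protocol 8.1: if an evaluable SD scan at least 4 weeks after the first PR comes before any confirming scan, that PR is not confirmed. A later pair of consecutive PRs can still confirm a response, with DoR dated from the first of that pair. If intervening NE or missing scans are to be tolerated, for PR or CR, say so and list it in SAP Section 2, since that also departs from the literal wording.

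**Alternative.** Keep the non-consecutive rule, amend protocol 8.1, list the rule in SAP Section 2, and report ORR and DoR under the consecutive rule as a sensitivity analysis in place of the present NA.

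Either way, use one interval throughout SAP 4.2.2.1: its general rule says not less than 4 weeks, its non-consecutive rule greater than 4 weeks. The first should be used.

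**Cost.** The preferred route takes one SAP paragraph and a small programming change, and the reported ORR may be slightly lower. The alternative adds a protocol amendment and the sensitivity outputs.
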